3.3 Rationale of dose/regimen, route of administration and duration of treatment

This extension study will assess the durability of the observed effect of bimagrumab upon treatment discontinuation. There is therefore no study drug administration as part of this study for patients enrolled following protocol amendment #1.

3.4 Rationale for choice of comparator

Not applicable.

3.5 Purpose and timing of interim analyses/design adaptations

An interim analysis will be triggered by the analysis of the core study Part A at the completion of Part A. This interim analysis will analyze key efficacy data. The results from the interim analysis, together with core study Part A and any additional data on the rest of the program, will be used for the next step decision making.

3.6 Risks and benefits

All patients in this study will participate in a structured, monitored, mildly intense exercise program designed to improve physical and emotional status in older adults with impaired physical function. In addition, results from the bimagrumab proof of concept study in

sarcopenic patients suggest that patients receiving active drug are likely to experience an increase in lean body mass and improvement in mobility performance. Given the half-life of bimagrumab, the effect is still expected to be present for an additional few weeks in the extension study after the last infusion.

Risks with bimagrumab

The risks of bimagrumab are not fully understood, but in healthy young, middle aged, and older adults and in patients with sporadic inclusion body myositis (sIBM) up through 78 years of age and in sarcopenic patients up to age 86, the drug was well tolerated and the AE profile was consistent across populations. Based on prior human studies there is a risk to participants of experiencing certain tolerability-related adverse events. The most common AEs include a transient skin condition (acne) and involuntary muscle contractions (i.e., twitches/spasms) as well as transient diarrhea. Transient increases in AST and ALT have been observed, sometimes in association with CK elevation (suggesting a muscle source) and sometimes not. Other observed adverse events (AEs) include arthralgia, muscle strain erythema and rash.

there have been no adverse cardiac findings in humans with current dose levels and regimens.

Refer to the Investigator's Brochure for a thorough evaluation of expected adverse events observed in clinical studies to date as well as data from in vivo pharmacology, animal toxicology, animal and human pharmacokinetic (PK), immunogenicity studies.

Blood draw risks

During the collection of blood samples, patients may experience pain and/or bruising at the insertion site of the needle/catheter. Although rare, localized clot formation, infections and nerve injury may occur. Lightheadedness and/or fainting may also occur during or shortly after the blood draw. Patients will be observed following all blood draws and discharged only when the Investigator observes stable health status. In addition, liquids by mouth in the form of water, fruit juice or a similar product will be provided following the blood draw to replenish the blood volume removed.

Imaging risks

This clinical study involves exposure to radiation from a DXA total body scan. The radiation exposure by DXA is not necessary for medical care but is intended for research purposes only. The total amount of radiation exposure per patient from DXA will be about 25 μ Sv. For effective radiation doses under 3 mSv (300 mrem), the risk is considered to be "minimal". Therefore, the radiation exposure in this study involves minimal risk and is necessary to obtain the research information desired (Njeh 1999). DXA measures are also described as having no observable or biological effect and are similar to natural background levels of radiation in most countries. Therefore, DXA scans within the study period need not be limited from a safety perspective.

Exercise-related injuries

During the study, the patients will be required to perform a prescribed set of exercises 2-3 times each week. The exercise program will involve warm-up (i.e., walking) and cool-down periods to improve comfort, prepare the body for increased effort, and reduce the risk of injury.

Some people participating in an exercise program may experience transient muscle soreness due to an increase in the volume and intensity of associated muscle contractions beyond their usual daily level. The risk of temporary muscle soreness will be reduced in these extension study participants as they will have already been participating in the exercise program for the full 8 month duration of the core study. In addition, the exercise programs will be tailored to each individual's level of fitness and interest during the evaluation and mid-study visit with the site staff.

4 Population

The study population will be community-dwelling men and women ages 70 years and older completing 24 weeks of treatment of the core study (CBYM338E2202 EOT visit) and willing to enter CBYM338E2202E1; these patients will be eligible providing they meet all inclusion and exclusion criteria of the extension protocol. No additional exclusions should be applied by the investigator. A relevant record (e.g., checklist) must be stored with the source documentation at the study site. Failure to meet any entry criterion excludes a patient from entering the post-treatment follow-up epoch.

It is expected that approximately 200 patients will participate in the extension study and that approximately 140 will complete it assuming a 30% drop out rate.

4.1 Inclusion criteria

Patients eligible for inclusion in this study have to fulfill all of the following criteria:

1. Men and postmenopausal women aged 70 years or older that have participated in, and have completed the full study treatment period per protocol (24 weeks/EOT visit) in the preceding core study (CBYM338E2202)
2. Written informed consent must be obtained before any assessment of the extension study is performed (can be obtained at the EOT visit of the core study).

4.2 Exclusion criteria

This is an extension study and has the same exclusions as the core study. Because only participants who complete the core study are eligible for inclusion in this study, patients who no longer qualify or should be discontinued from the core study are excluded from participating in this study. Patients fulfilling the following criterion are not eligible for inclusion in this study:

1. Any condition which should have led to treatment discontinuation per protocol in the core study

No additional exclusions may be applied by the investigator, in order to ensure that the study population will be representative of all eligible patients, within and across study sites.

5 Treatment

5.1 Protocol requested treatment

5.1.1 Investigational treatment

Patients newly enrolled after protocol amendment #1 will not receive any investigational treatment as part of this protocol.

For patients enrolled prior to protocol amendment #1 the investigational treatment is as follow:

- Bimagrumab [REDACTED] prepared by Novartis and supplied to the Investigator site as open labeled bulk medication.
- Placebo will be a Dextrose 5% in water infusion supplied by the site

Study drug preparation will be detailed in a separate pharmacy manual.

5.1.2 Additional study treatment

Dietary counseling will be performed to support daily intake levels of at least 0.8 g protein/kg and 20 kcals/kg of body weight throughout the study. If it is determined to be necessary from one of the planned diet assessments, patients will be instructed to consume a nutritional supplement to ensure adequate protein intake.

Even though patients enrolled based on protocol amendment #1 will not be exposed to bimagrumab or placebo, during this extension study, all enrolled patients in this study will receive specific study treatments as part of this protocol:

- Vitamin D supplementation
- Exercise program

The vitamin D3 (or D2 if D3 is not available) supplements will be locally sourced with a recommended dosage:

- daily administration of 800 IU to 4000 IU vitamin D3 (dose chosen by site based on patient need and country standard); or,
- equivalent weekly or monthly formulation if deemed to be of advantage for the individual patient's compliance.

Exercise program is presented in more details in [Section 3.1](#).

5.2 Treatment arms

Patients enrolled following protocol amendment #1 will not receive investigational treatment.

Patients enrolled prior to the protocol amendment #1 have been assigned to one of the following 2 treatment arms in a ratio of 1:1 to receive i.v. doses of the following and will continue with this treatment until their EOT:

1. Patients on BYM338 70 mg in core study were randomized 1:1 to receive either BYM338 70 mg or placebo (BYM 70/PBO) for 6 doses in the extension study
2. Patients on BYM338 210 mg in core study were randomized 1:1 to receive either BYM338 210 mg or placebo (BYM 210/PBO) for 6 doses in the extension study
3. Patients on BYM338 700 mg in core study were randomized 1:1 to receive either BYM338 700 mg or placebo (BYM 700/PBO) for 6 doses in the extension study
4. Patients on BYM338 0 mg (placebo) in core study were randomized 1:1 to receive BYM338 0 mg (placebo) in both arms for 6 doses in the extension study

5.3 Treatment assignment, randomization

Not applicable.

5.4 Treatment blinding

Patients as well as the site staff will remain blinded to core treatment allocation as well as the extension randomization code for patients enrolled prior to the extension protocol amendment #1 from the time of randomization in the core study CBYM338E2202 until the final database lock of the extension study CBYM338E2202E1. The Novartis core clinical study team will have access to the treatment codes after the interim analysis. Other Novartis team members in the countries will remain blinded until the final study data base lock.

The following methods will be used to maintain the blind: (1) Randomization data are kept strictly confidential until the time of un-blinding and will not be accessible by anyone else involved in the study except for the un-blinded pharmacist and the [REDACTED] bioanalyst. (2) Any potential visible difference in treatments will be concealed by the use of an opaque sleeve (applicable only for patients enrolled prior to amendment#1. (3) Any potentially unblinding parameters (e.g. DXA results) will not be available to the patient, site or study team, Randomization data are strictly confidential and will be accessible only to authorized personnel until un-blinding as described above. The study bioanalyst will receive a copy of the randomization schedule to facilitate analysis of the samples. Both the un-blinded pharmacist and bioanalyst will keep treatment allocation information confidential. Un-blinding will only occur in the case of patient emergencies (see [Section 5.5.13](#)) and as described above.

IMPORTANT for sites with patients enrolled prior to protocol amendment #1: Due to the difference in preparation methods between the active and placebo treatments, an un-blinded pharmacist who is independent of the study team will be required. This un-blinded pharmacist will receive the appropriate treatment allocation. Appropriate measures must be taken by the un-blinded pharmacist to ensure that the study team remains blinded throughout the course of dose administrations and the remainder of the study even in the follow-up epoch.

5.5 Treating the patient

5.5.1 Patient numbering

Patients in the extension study CBYM338E2202E1 will continue with the same uniquely identified patient number that was assigned in the core study.

As in the core study, the patient number is a combination of a four digit center number, which is provided by Novartis, and a three digit sequential number allocated by the investigator, starting with 001. Therefore, if the center number is 1001, the patient numbers will be assigned such as 1001001, 1001002, etc. in ascending order. If the center number is 1002, the patient numbers will be assigned such as 1002001, 1002002, etc.

Patients will be given the informed consent form (ICF) during one of the scheduled visits (e.g., Week 25 or at earlier visit) in study CBYM338E2202 to read and understand for their participation in this extension study. Patients will NOT be signing the ICF before completing the Week 25 (EOT) assessments of the core study.

Patients who are eligible based on the inclusion/exclusion criteria will be asked to sign the ICF. If the patient fails for any reason, he/she should not enter the extension and should complete the EoS visit of the core study as per the core study protocol.

5.5.2 Dispensing the investigational treatment

Section only applicable to patients enrolled prior to the protocol amendment#1.

The investigational drug, bimagrumab [REDACTED] will be prepared by Novartis and supplied to the Investigator's site as open labeled bulk medication.

Appropriate documentation of the patient specific dispensing process must be maintained.

Bulk medication labels will be in the local language, will comply with the legal requirements of each country, and will include storage conditions for the drug but no information about the patient.

5.5.3 Handling of study treatment

5.5.3.1 Handling of investigational treatment

For patients enrolled prior to protocol amendment#1 only

Investigational treatment must be received at the study site by a designated person, handled and stored safely and properly, and kept in a secured location to which only the Investigator and designated staff have access. Upon receipt, the study drugs should be stored according to the instructions specified on the labels. Clinical supplies are to be dispensed only in accordance with the protocol. Technical complaints are to be reported to the respective Novartis CPO Quality Assurance representative. Storage conditions must be adequately monitored and appropriate temperature logs maintained as Source data.

The Investigator must maintain an accurate record of the shipment and dispensing of study drug in a drug accountability ledger. Drug accountability will be noted by the un-blinded Monitor during site visits and/or at the completion of the trial.

All drug supplies are to be used only for this protocol and not for any other purpose. Unless specifically instructed by Novartis, the Investigator must not destroy any drug labels, or any used, partly used or unused drug supply.

At the conclusion of the study, and, if allowed during the course of the study (e.g., the un-blinded monitor), the Investigator will provide a copy of the drug accountability ledger to the Monitor.

Only after receiving a written authorization by Novartis, the Investigator/designee will send all the unused and partly used drug supplies as well as the empty containers to the address provided at the time of authorization for destruction or have the unused and partly used drug supplies as well as the empty containers destroyed by the site's pharmacist, providing a drug destruction certificate (appropriate local SOP must be in place).

For ALL patients enrolled in the study

As in the core study, to avoid Vitamin D deficiency during the extension study, all patients will continue to receive vitamin D3 supplementation (or D2 if D3 is not possible) (800 IU-4000 IU per day) from the start of the study to the EOS visit. The vitamin D supplements will be locally sourced.

For more details refer to [Section 5.1.2](#).

5.5.4 Instructions for prescribing and taking study treatment

Section only applicable to patients enrolled prior to the protocol amendment#1.

[REDACTED]
[REDACTED] End of infusion

will be considered as the time of the end of the line flush. All times stated within this protocol are from the start of study drug administration (unless otherwise stated).

Infusions will occur every 4 weeks, after all pre-dose assessments have been performed. Six doses will be administered during the course of the study (see [Section 3.1](#)).

Only the materials (infusion bag, administration set and filter) specified in the pharmacy manual should be used for administration of the study medication.

All dosages prescribed and dispensed to the patient during the study must be recorded on the Dosage Administration Record electronic case report form (eCRF) page.

5.5.5 Permitted dose adjustments and interruptions of study treatment

Section only applicable to patients enrolled prior to the protocol amendment#1.

Study drug dose adjustments are not permitted.

Study drug interruptions or dosing delays should be avoided wherever possible and should occur within the given window as detailed in the [Section 6](#) and [Table 6-2](#).

If a patient misses two doses the patient must be discontinued from investigational treatment (refer to [Section 5.5.10](#))

5.5.6 Recommended treatment of adverse events

Acne may be treated with a face wash containing 4-10% benzoyl peroxide wash and over the counter topical treatments. On occasion, a prescription topical treatment (i.e., antibiotics) or oral antibiotic (i.e., minocycline 100 mg b.i.d.) may be recommended at the Investigator's discretion. Early intervention is recommended when acne presents.

Muscle symptoms can be addressed with light self-massage of the involved area concentrating on improving circulation and relaxing muscle tissue. If excessive or prolonged soreness presents, then acetaminophen may be used as needed.

Medication used to treat AEs must be recorded on the Concomitant medications/Significant non-drug therapies eCRF.

Although not expected, any acute allergic reactions should be treated as needed using conventional counter measure therapies as indicated (including but not limited to epinephrine, antihistamine, corticosteroid, intravenous supplies, crystalloid, an oral airway, bag and mask, and supplemental oxygen). In the case of a serious adverse event in which decreasing the systemic concentration of bimagrumab may be of clinical benefit, the investigator should consider plasmapheresis.

5.5.7 Rescue medication

Not applicable, as there are no approved pharmacotherapies for sarcopenia.

[figure not shown]
5.5.8 Concomitant treatment

The investigator should instruct the patient to notify the study site about any new medications he/she takes after the start of the study. All prescription medications, over-the-counter drugs and significant non-drug therapies (including physical therapy and blood transfusions) administered or taken within the timeframe defined in the entry criteria prior to the start of the study and during the study, must be recorded on the prior and concomitant medications or on the surgical and medical procedures eCRF pages.

5.5.9 Prohibited treatment

Any investigational treatment on a different protocol is forbidden at the time of enrollment or within 5 half-lives of the investigational treatment prior to enrollment.

Use of the treatments displayed in the table below are NOT allowed throughout the extension study). The following treatments are not allowed because of their biological effect on muscle anabolism or catabolism, which would potentially confound the assessment of efficacy.

5.5.10 Discontinuation of study treatment or from study

For patients enrolled prior to the protocol amendment#1.

Individual subject discontinuation

The investigator should discontinue study treatment for a given patient if, on balance, he/she believes that continuation would be detrimental to the subject's well-being.

Investigational treatment must be discontinued under the following circumstances:

- Use of prohibited treatment as per [Table 5-1](#).
- Any other protocol deviation that results in a significant risk to the patient's safety
- Breaking of the blind (inadvertently or for emergency reasons)
- Severe hypersensitivity reaction occurs

- Liver event definition met as per [Appendix 1](#)
- Total of two (2) doses were missed in the entire study
- Death
- Withdrawal of consent
- Sponsor decision to terminate (part of) the study

Investigational treatment may be discontinued under the following circumstances:

- Emergence of one or more adverse events that in the judgment of the investigator, taking into account the patient's overall status, prevent the patient from safely continuing in the study
- Any laboratory abnormalities that in the judgment of the investigator, taking into consideration the patient's overall status, prevents the patient from safely continuing in the study

Patients who discontinue study treatment should NOT be considered withdrawn from the study UNLESS they withdraw their consent (see [Section 5.5.11](#)). They should return as close to 28 days since the last dose received and complete the EOT visit and enter the Post-treatment follow up. The EOS visit should be scheduled 4 weeks after EOT. If they fail to return for these visits for unknown reasons, every effort should be made to contact them as specified in [Section 5.5.12](#).

At a minimum, patients will be contacted for safety evaluations during the 30 days following the last study visit, including a final contact at the 30-day point. Documentation of attempts to contact the patient should be recorded in the source documentation. Investigators or site personnel must contact the IRT to register the patient's discontinuation from treatment.

For patients enrolled after the protocol amendment#1.

Patients have to be discontinued from the study if they receive any of the prohibited medication listed in Section 5.5.9.

Patient can be discontinued if in the judgment of the investigator, taking into account the patient's overall status prevents the patient from safely continuing in the study.

Patients should then return to the site to perform the EOS visit as soon as possible and not later than 4 weeks after the decision being taken.

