7.3 Liver safety monitoring

To ensure subject safety and enhance reliability in determining the hepatotoxic potential of an investigational drug, a standardized process for identification, monitoring and evaluation of liver events has to be followed.

Liver events are divided into two categories:

- Liver events of special interest (AESI) which consist of elevated transaminases and/or bilirubin (elevated liver function tests (LFTs)).
- Medically significant liver events which are considered as serious adverse events (SAEs) and which consist of marked elevations of LFTs and / or pre-specified adverse events.

Please refer to [Table 13-1-Appendix 1](#) for complete definitions of liver events.

Any liver event which meets the criteria for a "medically significant" event should follow the standard procedures for SAE reporting as described in [Section 7.2](#).

Every liver event as defined in [Table 13-1-Appendix 1](#) should be followed up by the investigator or designated personal at the trial site, as summarized below and detailed in [Table 13-1-Appendix 1](#).

- Repeating the LFT to confirm elevation as appropriate
- Discontinuation of the investigational drug if appropriate
- Hospitalization of the subject if appropriate
- A causality assessment of the liver event via exclusion of alternative causes (e.g., disease, co-medications)
- An investigation of the liver event which needs to be followed until resolution.

These investigations can include serology tests, imaging and pathology assessments, hepatologist's consultancy, based on investigator's discretion. All follow-up information, and the procedures performed should be recorded as appropriate in the CRF.

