9.1 Analysis sets

Full analysis set (FAS): The FAS comprises all subjects enrolled in the study..

Safety set (SAF): The safety set comprises all subjects who received at least one dose of study drug from the core or extension study and enrolled in the extension study.

Per-protocol set (PP): The Per-protocol set comprises all subjects in the FAS who do not have major protocol deviations that could confound the interpretation of analyses conducted on the FAS. The following are common examples of such protocol deviations:

- Subject entered the study even though they did not satisfy the entry criteria
- Subject developed study/treatment withdrawal criteria during the study but was not withdrawn
- Subject received the wrong treatment or incorrect dose
- Subject took a prohibited concomitant medication

The PP set will be identified and finalized based on blinded review of the data, prior to the database lock.

To facilitate different analysis on patients enrolled before and after the protocol amendment, two populations are defined as in below:

- Population I is defined to include patients enrolled prior to protocol amendment 1, who will be continuing the treatment as originally assigned and follow the original schedule until end of the study.
- Population II is defined to include patients enrolled after protocol amendment 1, who will be followed up per schedule defined in this protocol amendment.

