LIVER LABORATORY TRIGGERS	
• $3 \times \text{ULN} < \text{ALT} / \text{AST} \leq 5 \times \text{ULN}$• $1.5 \times \text{ULN} < \text{TBL} \leq 2 \times \text{ULN}$
LIVER EVENTS	
• $\text{ALT or AST} > 5 \times \text{ULN}$• $\text{ALP} > 2 \times \text{ULN}$ (in the absence of known bone pathology)• $\text{TBL} > 2 \times \text{ULN}$ (in the absence of known Gilbert syndrome)• $\text{ALT or AST} > 3 \times \text{ULN}$ and $\text{INR} > 1.5$• Potential Hy's Law cases (defined as $\text{ALT or AST} > 3 \times \text{ULN}$ and $\text{TBL} > 2 \times \text{ULN}$ [mainly conjugated fraction] without notable increase in ALP to $> 2 \times \text{ULN}$)• Any clinical event of jaundice (or equivalent term)• $\text{ALT or AST} > 3 \times \text{ULN}$ accompanied by (general) malaise, fatigue, abdominal pain, nausea, or vomiting, or rash with eosinophilia• Any adverse event potentially indicative of a liver toxicity *

Table 13-2 Follow Up Requirements for Liver Events and Laboratory Triggers

Criteria	Actions required	Follow-up monitoring
Potential Hy's Law case ^a	
 Discontinue the study drug immediately Hospitalize, if clinically appropriate Establish causality Complete liver CRF 	ALT, AST, TBL, Alb, PT/INR, ALP and γ GT until resolution ^c (frequency at investigator discretion)
ALT or AST		
> 8 × ULN	
 Discontinue the study drug immediately Hospitalize if clinically appropriate Establish causality Complete liver CRF 	ALT, AST, TBL, Alb, PT/INR, ALP and γ GT until resolution ^c (frequency at investigator discretion)
> 3 × ULN and INR > 1.5	
 Discontinue the study drug immediately Hospitalize, if clinically appropriate Establish causality Complete liver CRF 	ALT, AST, TBL, Alb, PT/INR, ALP and γ GT until resolution ^c (frequency at investigator discretion)
> 5 to ≤ 8 × ULN	
 Repeat LFT within 48 hours If elevation persists, continue follow-up monitoring If elevation persists for more than 2 weeks, discontinue the study drug Establish causality Complete liver CRF 	ALT, AST, TBL, Alb, PT/INR, ALP and γ GT until resolution ^c (frequency at investigator discretion)

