> 3 × ULN accompanied by symptoms ^b	
 Discontinue the study drug immediately Hospitalize if clinically appropriate Establish causality Complete liver CRF 	ALT, AST, TBL, Alb, PT/INR, ALP and γ GT until resolution ^c (frequency at investigator discretion)
> 3 to ≤ 5 × ULN (patient is asymptomatic)	
 Repeat LFT within the next week If elevation is confirmed, initiate close observation of the patient 	Investigator discretion Monitor LFT within 1 to 4 weeks
ALP (isolated)		
> 2 × ULN (in the absence of known bone pathology)	
 Repeat LFT within 48 hours If elevation persists, establish causality Complete liver CRF 	Investigator discretion Monitor LFT within 1 to 4 weeks or at next visit
TBL (isolated)		
> 2 × ULN (in the absence of known Gilbert)	
 Repeat LFT within 48 hours If elevation persists, discontinue 	ALT, AST, TBL, Alb, PT/INR, ALP and γ GT until resolution ^c (frequency at investigator discretion)

Criteria	Actions required	Follow-up monitoring
syndrome)	the study drug immediately 
 • Hospitalize if clinically appropriate • Establish causality • Complete liver CRF 	discretion) Test for hemolysis (e.g., reticulocytes, haptoglobin, unconjugated [indirect] bilirubin)
> 1.5 to ≤ 2 × ULN (patient is asymptomatic)	
 • Repeat LFT within the next week • If elevation is confirmed, initiate close observation of the patient 	Investigator discretion Monitor LFT within 1 to 4 weeks or at next visit
Jaundice	
 • Discontinue the study drug immediately • Hospitalize the patient • Establish causality • Complete liver CRF 	ALT, AST, TBL, Alb, PT/INR, ALP and γGT until resolution ^c (frequency at investigator discretion)
Any AE potentially indicative of a liver toxicity*	
 • Consider study drug interruption or discontinuation • Hospitalization if clinically appropriate • Establish causality • Complete liver CRF 	Investigator discretion

*These events cover the following: hepatic failure, fibrosis and cirrhosis, and other liver damage-related conditions; the non-infectious hepatitis; the benign, malignant and unspecified liver neoplasms

^aElevated ALT/AST > 3 × ULN and TBL > 2 × ULN but without notable increase in ALP to > 2 × ULN

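### For Population I, Protocol 5.5.10 makes every Appendix 1 liver event a mandatory stop, while Table 13-2 makes stopping delayed, conditional, optional or absent for some of the same events

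*Protocol*

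**What the plan says.** Protocol 5.5.10 opens with a block headed "For patients enrolled prior to the protocol amendment#1" and states: "Investigational treatment must be discontinued under the following circumstances". One item on that list is "Liver event definition met as per" Appendix 1. It carries no condition on severity, persistence or investigator judgement. A separate list in the same section gives circumstances in which treatment *may* be stopped, and that is where adverse events and laboratory abnormalities left to the investigator's judgement appear.

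Appendix 1 has two tables. Table 13-1 defines liver events. Table 13-2 gives the action for each finding. For ALT or AST above 5 and up to 8 x ULN, the tests are repeated within 48 hours, then "If elevation persists, continue follow-up monitoring"; the drug is stopped only if the elevation lasts more than 2 weeks. For an adverse event potentially indicative of liver toxicity, the instruction is "Consider study drug interruption or discontinuation".

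Protocol 7.3, which covers every liver event, lists "Discontinuation of the investigational drug if appropriate".

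On the analysis side, Protocol 9.1 and SAP 3.1 both give this as an example of a deviation that can remove a patient from the per-protocol set: "Subject developed study/treatment withdrawal criteria during the study but was not withdrawn".

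**The concern.** A stopping rule has to give one answer for one finding. Here an investigator who follows Table 13-2 to the letter can keep a patient on drug when 5.5.10 says treatment must end. Protocol 3.6 reports transient AST and ALT increases with bimagrumab, so the situation is foreseeable.

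Two things are at stake. The first is consistent safety handling across sites for patients still receiving infusions. The second is classification: the per-protocol definition refers to withdrawal criteria, and the protocol contains two versions of what those criteria are for liver events. A patient handled correctly under one page could be recorded as a deviation under another.

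**Working it through.** The plan states no figure on this point, so the check sets each Table 13-1 definition beside its Table 13-2 action and compares both with 5.5.10.

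| Table 13-1 liver event | 5.5.10 | Table 13-2 | Same outcome? |
|---|---|---|---|
| ALT/AST >3 x ULN with INR >1.5 | must stop | stop immediately | yes |
| Potential Hy's Law case | must stop | stop immediately | yes |
| ALT/AST >3 x ULN with symptoms | must stop | stop immediately | yes |
| Jaundice | must stop | stop immediately | yes |
| ALT/AST >5 x ULN | must stop | above 8: stop immediately; above 5 up to 8: repeat, monitor, stop if it lasts more than 2 weeks | only above 8 |
| TBL >2 x ULN (isolated) | must stop | repeat within 48 hours, stop if it persists | no |
| ALP >2 x ULN (isolated) | must stop | repeat, establish causality, complete liver CRF; no stopping instruction | no |
| AE potentially indicative of liver toxicity | must stop | consider interruption or discontinuation | no |

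Count: 4 agree + 3 differ + 1 differs in part = 8. The exceptions inside the definitions do not remove the mismatch. The ALP entry, for example, applies "in the absence of known bone pathology" in both tables, so the same patient meets the definition and falls under the action row.

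Who is reached:
- The mandatory list applies only to patients enrolled before Amendment 1. Protocol 5.1.1 says later patients receive no investigational treatment, and the part of 5.5.10 written for them has no liver rule.
- The Amendment 1 rationale puts Population I at about 45 patients, with 10 to 15 expected to be ongoing at implementation: 10/45 = 22% to 15/45 = 33%.

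Which analyses are reached:
- Protocol 9.4.2 bases all efficacy analyses on the full analysis set, which is everyone enrolled (9.1), and plans no formal hypothesis test. Classifying a patient under one liver rule or the other does not change that set.
- The per-protocol set is supportive (Protocol 9.4.4) and is left out of the interim analysis (SAP 3.8).
- SAP 6.1 says the list of deviations, with the analysis sets each removes a patient from, is to be defined before unblinding, so the outcome is still open.

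How much one reclassified patient could matter: Protocol 5.2 splits each of three bimagrumab doses into two groups and has a continued placebo group, 3 x 2 + 1 = 7. An equal split, which the documents do not state and which is used only for illustration, gives 45/7 = 6.4 patients per group. One patient moved out of the per-protocol set could then be about one in six of a group. The documents give no liver event rate, so the expected number of such patients cannot be calculated.

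**The case against.** The strongest reply is that these are stricter and looser wordings, not impossible instructions. A site that always stopped would break nothing in the ALP row, the *consider* row or Section 7.3. That is true, and a reader who infers that the passages cannot all be obeyed goes too far for those three texts. The reply works in one direction only, however: a site that follows Table 13-2 exactly can breach the *must* in 5.5.10.

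A second reply is that pointing to Appendix 1 brings in the graded actions of Table 13-2. But the trigger in 5.5.10 is the definition being met, and the definitions are in Table 13-1. Even if the actions were brought in, a mandatory stop would not fit a row with no stop or a row that only asks the investigator to consider one.

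A third reply is that the practical gap is narrow. Section 5.5.10 gives no timing. Infusions are 4 weeks apart (5.5.4), so a 48-hour repeat or a two-week persistence check would usually finish before the next dose, and persistent ALT/AST or bilirubin elevations end in a stop under both texts. Six doses from day 1 end on day 141 (1 + 5 x 28), so of the draws that Appendix 2 schedules on days 29, 85, 169 and 197, only the first two precede a remaining dose. This stands and limits the size. What is left is elevations that resolve, isolated ALP and the optional adverse-event row, together with any unscheduled tests.

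A reader might also infer that the conflict changes who was eligible, because SAP 6.1 Exclusion 5 cites Appendix 1. The documents do not show this. Protocol exclusion criterion 1 (4.2) refers to stopping conditions in the core study protocol, which is not among the documents. Exclusion 5 also concerns stopping in the core study and cites Appendix 1, not 5.5.10.

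**Conclusion.** The inconsistency is real and sits in current text, and it should be corrected. Three of the eight liver event definitions (TBL, ALP, liver adverse events) and part of a fourth (ALT/AST, up to 8 x ULN) have different consequences in 5.5.10 and Table 13-2. It concerns Population I only.

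The analysis consequence is possible, not certain. It would be tempting to say that a patient managed under Table 13-2 is a per-protocol exclusion. The protocol gives the withdrawal-criteria item as an example of deviations that could confound interpretation, to be settled by blinded review, so exclusion is not automatic. Full analysis set results are unaffected by the classification. Nothing supports a wider effect on eligibility or Population II.

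This rests on reading the liver item in 5.5.10 as it is written, without an implied persistence or judgement condition. No view is taken on which stopping rule is right.

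**What to change.** Reconcile Protocol 5.5.10, 7.3, Table 13-1 and Table 13-2 so that each liver event has one stated consequence, worded the same way wherever it appears. The sponsor's clinical team decides what that consequence is.

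In the SAP, tie the per-protocol deviation for unmet withdrawal criteria to that single text, and record in the SAP 6.1 deviation list whether a patient managed under Table 13-2 before the clarification counts as a deviation. Do this before unblinding. Protocol 5.4 gives the sponsor's core clinical team the treatment codes after the interim analysis, so a written rule fixed before then is safer than case-by-case decisions later.

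The cost is a protocol clarification and a matching SAP cross-reference. No assessment, sample size or analysis method changes.
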